8.6.3. Laboratory Evaluations

Selected laboratory data will be summarized (n, mean, SD, median, Q1, Q3, minimum, and maximum) along with corresponding changes. The incidence of treatment-emergent graded laboratory abnormalities will be summarized similarly.

Graded laboratory abnormalities will be defined using CTCAE 4.03 grading scale in [Appendix 4](#).

Laboratory abnormalities that occur before the first dose of study drug or after the subject has been discontinued from treatment for at least 30 days will be included in a data listing.

8.6.4. Other Safety Evaluations

Individual data for physical examination findings, prior and concomitant medications and medical history will be provided. Vital signs measurements will be listed by subject and summarized by incidence of events/abnormalities or descriptive statistics as appropriate.

8.7. Pharmacokinetic Analysis

Plasma concentrations and other PK parameters of filgotinib, the active metabolite of filgotinib (GS-829845) and GS-9876 will be listed and summarized using descriptive statistics (eg, sample size, arithmetic mean, geometric mean, % coefficient of variation, standard deviation, median, minimum, and maximum). Plasma concentrations of other filgotinib or GS-9876 metabolite(s) may also be determined and analyzed.

Urine PK analyses may be performed for GS-9876, filgotinib and its active metabolite, GS-829845, using the 24h urine collection at Week 16.

8.8. Biomarker Analysis

CCI

A large rectangular area of the page is completely blacked out, indicating redacted content. The text 'CCI' is printed in red at the top left corner of this redacted area.

For biomarker analysis, the baseline level and the modulation pattern upon treatment, including change over time from baseline level, will be evaluated by treatment arm. Descriptive statistics will be provided at each sampling time, by treatment arm. Additionally graphical summaries, eg, mean \pm SD, median \pm interquartile range (Q1, Q3), box plots, and scatter plots to explore correlations between different biomarkers may also be generated, as needed. These graphs may be generated for raw values as well as changes, as appropriate.

CCI

Biomarker objectives may be further described and updated based on evolving scientific knowledge of filgotinib and GS-9876. CCI

8.9. Sample Size

The sample size was chosen based on the practical considerations and to ensure that a clinically meaningful reduction in proteinuria from Baseline (Day 1) could be detected in any of the treatment groups, filgotinib or GS-9876. With 16 subjects per treatment group (32 subjects total), there is a 80% power to detect a 35% reduction from Baseline (Day 1) in proteinuria at Week 16 with a standard deviation of 50% and a 2-sided 0.05 significance level.

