 - d) Aspartate aminotransferase (AST) or alanine aminotransferase (ALT) > 3 times the upper limit of normal range (ULN) AND total bilirubin $> 2 \times$ ULN or accompanied by symptoms consistent with hepatic injury¹
 - e) AST and/or ALT elevations $> 3 \times$ ULN accompanied by elevated international normalized ratio (INR)¹
 - f) AST or ALT $> 5 \times$ ULN¹
 - g) Estimated glomerular filtration rate (eGFR_{MDRD}) < 40 mL/min/1.73 m² based on the MDRD formula

Subjects who discontinue study drug dosing at any time may continue with study visits, procedures, and assessments, if deemed medically appropriate by the investigator, but will not be eligible for entering the 20-week Extended Blinded Treatment Phase. Subjects who permanently discontinue study medication for any reason will not be replaced. Subjects withdrawing from the study should complete the early termination (ET) and Final FU visits. Subjects are free to withdraw from the study at any time without providing reason(s) for withdrawal and without prejudice to further treatment. The reason(s) for withdrawal will be documented in the electronic case report form (eCRF).

¹ In each case, there is a need for additional investigations, such as review of ethanol, recreational drug and dietary supplement consumption; testing for acute hepatitis A, B or C infection and biliary tract imaging should be promptly discussed with the study medical monitor.

Reasonable efforts will be made to contact subjects who are lost to follow-up. All contacts and contact attempts must be documented in the subject's file.

The sponsor has the right to terminate the study at any time in case of safety concerns or if special circumstances concerning the study medication or the company itself occur, making further treatment of subjects impossible. In this event, the investigator(s) and relevant authorities will be informed of the reason for study termination.

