8.5.1. Primary Analysis

The primary endpoint, the percent change from Baseline (Day 1) in 24-hour proteinuria at Week 16, will be calculated and the 95% confidence interval will be constructed for each treatment group.

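### The 80% power stated for 16 subjects per group holds only if the SD is treated as known; a t-based analysis at the same inputs has about 74% power

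*Protocol*

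**What the plan says.** Protocol 8.9 gives the design basis. For a group size of 16 (32 in all) it states that "there is a 80% power to detect a 35% reduction from Baseline (Day 1) in proteinuria at Week 16". The SD assumed for the percent change is 50%, and the test level is 0.05, two-sided. The reduction is one that "could be detected in any of the treatment groups, filgotinib or GS-9876", so the power refers to change from baseline within an arm and not to a comparison between arms. The same section also cites practical considerations. The synopsis (Statistical Methods) and SAP 1.3 carry the same power statement. None of the three places names the test or formula.

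Protocol 8.5.1 plans the primary analysis as the percent change in 24-hour proteinuria at Week 16, for which "the 95% confidence interval will be constructed for each treatment group". The interval method is not named. SAP 6.1.1 tests no hypothesis and SAP 6.1.2 plans descriptive statistics only. SAP 1.3 adds that enrolment stopped after 9 subjects were randomized.

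**The concern.** A power figure is meaningful only for a particular analysis. Here the sample size, the power and the significance level are all stated and the analysis is not. With 16 subjects, the gap between a calculation that takes the SD as known and one that estimates it from the data is too large to pass as rounding. If the figure comes from the known-SD formula, the design as described does not deliver 80% at a true two-sided 0.05, and the error is in the favourable direction.

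What is at stake is the record of the design basis. SAP 1.3 was written after enrolment stopped and still gives the 80% in the present tense. The SAP supports the abbreviated study report, so the figure could pass into that report or be reused to size a later study on similar assumptions.

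**Working it through.** **Inputs (Protocol 8.9):** n = 16 per group; mean reduction 35 percentage points; SD of percent change 50 percentage points; two-sided alpha 0.05. The comparison is within group, so this is a one-sample problem. The 1:1 allocation does not enter.

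**Step 1. Standardized effect.** d = 35/50 = 0.7. Noncentrality = 0.7 × √16 = 2.8.

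**Step 2. Reproduce the plan's figure (known SD, normal).** Power = Φ(2.8 − 1.96) = Φ(0.84) = 79.96%. Solving for the sample size, n = ((1.96 + 0.8416)/0.7)² = 16.02. Both match the plan's 80% and 16.

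**Step 3. Try other readings at n = 16.**

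| Reading | Power |
|---|---|
| One-sample t, two-sided 0.05 | 74.5% |
| One-sample t, one-sided 0.05 | 84.7% |
| One-sample z, one-sided 0.05 | 87.6% |
| Two-sample z | 50.8% |
| Two-sample t | 48.3% |
| Log scale, ln(0.65), assumed log-SD 0.5: z / t | 93.1% / 89.6% |
| At least one of the two arms significant: z / t | 96.0% / 93.5% |

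None comes within 2 points of 80%. The known-SD normal formula is therefore the only source found for the figure.

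**Step 4. Power with the SD estimated.** One-sample t with 15 df has critical value 2.131. With noncentrality 2.8 the noncentral t distribution gives 74.45%. A simulation of 400,000 normal samples gave 74.4%. A t-based 95% interval excluding zero is the same event, so it has the same power. The shortfall is 79.96 − 74.45 = 5.5 points, and the type II error rises from 20% to 25.5%.

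**Step 5. Can 1.96 be kept?** If 1.96 is used with an estimated SD, power is 79.5%. The actual two-sided alpha is then 2 × P(t₁₅ > 1.96) = 6.9%, and the coverage of the interval is 93.1%. That restores the power by giving up "a 2-sided 0.05 significance level" and the nominal 95% coverage.

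**Step 6. What would give 80% on the t basis.**

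| n per group | t-based power |
|---|---|
| 16 | 74.5% |
| 17 | 77.3% |
| 18 | 79.9% |
| 19 | 82.3% |

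At n = 16, 80% needs d of about 0.75, that is a 37.5% reduction with SD 50%, or a 35% reduction with SD 46.7%.

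**Step 7. Fewer evaluable subjects (illustration only).** Protocol 8.9 gives no dropout allowance. With 15 evaluable subjects t-based power would be 71.3%, and with 14 it would be 67.8%.

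**The case against.** The strongest reply is that nothing was miscalculated. The stated inputs return 79.96% by a standard planning formula, and the sentence makes the power conditional on an SD of 50%. On this view the point concerns method and disclosure. It is true that the arithmetic inside the formula is correct. But a planning SD is always assumed, while the analysis must use the SD observed in 16 subjects. The power that matters is that of the analysis, and it is not 80%.

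Second, the normal formula is inferred, and so is the t-based comparator: neither document names a test or an interval method. That is correct. The inference rests on the close match of both power and n, and a t-based interval is the ordinary reading of a 95% interval for a mean at this size. The conclusion does not depend on how the sponsor reached 80%.

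Third, the 74.5% assumes normally distributed percent changes. A normal distribution with mean −35 and SD 50 puts about 10% of its mass below −100%, which proteinuria cannot reach. The assumption should be stated, but it does not rescue the figure. With a lognormal ratio of the same mean and SD, t-based power is about 73.7%.

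Fourth, the lower powers for 15 and 14 subjects do not follow from the protocol. Section 3.5.2 says "Subjects who permanently discontinue study medication for any reason will not be replaced", but it also lets subjects who stop drug remain in the visit schedule, and the Full Analysis Set keeps every dosed randomized subject. Stopping drug is not the same as having no Week 16 value. This stands, and those figures are only an illustration.

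Finally, no current decision depends on the figure, and the size also rested on practical grounds. Both are true. They limit the importance of the error without making the number right.

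**Conclusion.** The concern holds, as a minor point. With n = 16, d = 0.7 and a true two-sided 0.05, a mean-based analysis that estimates the SD has 74.5% power against the 80% stated. Sixteen subjects, 80% power and alpha 0.05 are compatible only if the SD is known. The gap equals two to three more subjects per group.

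The result assumes approximately normal percent changes, all 16 subjects evaluable at Week 16, and a one-sample t-test or t-based interval as the analysis. The use of the normal formula is a strong inference and is not documented.

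The SAP does not claim 80% for the 9 subjects randomized, and this point does not suggest that it does. It corrects the record of the design basis and leaves the planned descriptive analysis unchanged.

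**What to change.** Change the power sentence in the synopsis, Protocol 8.9 and SAP 1.3 in one of two ways:

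- Restate it, for example: *With 16 evaluable subjects per group, a two-sided 0.05 one-sample t-test of within-group percent change has about 74% power for a 35% reduction, assuming an SD of 50% and approximate normality.*
- Keep the 80%, label it a normal approximation with known SD, and give the t-based figure of about 74% beside it. This preserves the rationale on which 16 per group appears to have been chosen.

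Optionally, SAP 1.3 can note that the planned power does not apply at the size achieved. Any precision figure added there should state the arm split, the number evaluable and the SD assumed.

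The cost is wording only, with no extra patients and no change to the analysis. If the protocol will not be amended again, correcting SAP 1.3 alone is sufficient.

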8.10. Data Monitoring Committee

An external multidisciplinary DMC will review the progress of the study and perform interim reviews of safety data and provide recommendation to Gilead whether the nature, frequency, and severity of adverse effects associated with study treatment warrant the early termination of the study in the best interests of the participants, whether the study should continue as planned, or the study should continue with modifications.

The first DMC data review meeting will be conducted after approximately 50% of planned subjects enroll and complete through 16 weeks of study treatment. The DMC's specific activities will be defined by a mutually agreed charter, which will define the DMC's membership, conduct and meeting schedule.

While the DMC will be asked to advise Gilead regarding future conduct of the study, including possible early study termination, Gilead retains final decision-making authority on all aspects of the study.

8.11. Analysis Schedule

The primary and secondary analyses will be conducted after all subjects either complete their Week 16 visit or prematurely discontinue from the study. The final analysis will be performed when all subjects complete the study or prematurely discontinue from the study.

9. RESPONSIBILITIES

9.1. Investigator Responsibilities

9.1.1. Good Clinical Practice

The investigator will ensure that this study is conducted in accordance with the principles of the Declaration of Helsinki, International Council for Harmonisation (ICH) guidelines, or with the laws and regulations of the country in which the research is conducted, whichever affords the greater protection to the study subject.

The investigator will ensure adherence to the basic principles of Good Clinical Practice, as outlined in 21 CFR 312, subpart D, "Responsibilities of Sponsors and Investigators," 21 CFR, part 50, and 21 CFR, part 56.

The investigator and all applicable subinvestigators will comply with 21 CFR, Part 54, providing documentation of their financial interest or arrangements with Gilead, or proprietary interests in the investigational drug under study. This documentation must be provided prior to the investigator's (and any subinvestigator's) participation in the study. The investigator and subinvestigator agree to notify Gilead of any change in reportable interests during the study and for 1 year following completion of the study. Study completion is defined as the date when the last subject completes the protocol-defined activities.

9.1.2. Institutional Review Board (IRB)/Independent Ethics Committee (IEC) Review and Approval

The investigator (or sponsor as appropriate according to local regulations) will submit this protocol, informed consent form, and any accompanying material to be provided to the subject (such as advertisements, subject information sheets, or descriptions of the study used to obtain informed consent) to an IRB. The investigator will not begin any study subject activities until approval from the IRB has been documented and provided as a letter to the investigator.

Before implementation, the investigator will submit to and receive documented approval from the IRB any modifications made to the protocol or any accompanying material to be provided to the subject after initial IRB approval, with the exception of those necessary to reduce immediate risk to study subjects.

9.1.3. Informed Consent

The investigator is responsible for obtaining written informed consent from each individual participating in this study after adequate explanation of the aims, methods, objectives, and potential hazards of the study and before undertaking any study-related procedures. The investigator must use the most current IRB-approved consent form for documenting written informed consent. Each informed consent (or assent as applicable) will be appropriately signed and dated by the subject or the subject's legally authorized representative and the person

conducting the consent discussion, and also by an impartial witness if required by IRB local requirements. **CCI**

9.1.4. Confidentiality

The investigator must assure that subjects' anonymity will be strictly maintained and that their identities are protected from unauthorized parties. Only subject initials, date of birth, another unique identifier (as allowed by local law) and an identification code will be recorded on any form or biological sample submitted to the Sponsor, IRB, or laboratory. Laboratory specimens must be labeled in such a way as to protect subject identity while allowing the results to be recorded to the proper subject. Refer to specific laboratory instructions. NOTE: The investigator must keep a screening log showing codes, names, and addresses for all subjects screened and for all subjects enrolled in the trial. Subject data will be processed in accordance with all applicable regulations.

The investigator agrees that all information received from Gilead, including but not limited to the investigator brochure, this protocol, CRF/eCRF, the IMP, and any other study information, remain the sole and exclusive property of Gilead during the conduct of the study and thereafter. This information is not to be disclosed to any third party (except employees or agents directly involved in the conduct of the study or as required by law) without prior written consent from Gilead. The investigator further agrees to take all reasonable precautions to prevent the disclosure by any employee or agent of the study site to any third party or otherwise into the public domain.

9.1.5. Study Files and Retention of Records

The investigator must maintain adequate and accurate records to enable the conduct of the study to be fully documented and the study data to be subsequently verified. These documents should be classified into at least the following two categories: (1) investigator's study file, and (2) subject clinical source documents.

The investigator's study file will contain the protocol/amendments, CRF and query forms, IRB and governmental approval with correspondence, informed consent, drug records, staff curriculum vitae and authorization forms, and other appropriate documents and correspondence.

The required source data should include sequential notes containing at least the following information for each subject:

- Subject identification (name, date of birth, gender);
- Documentation that subject meets eligibility criteria, ie, history, physical examination, and confirmation of diagnosis (to support inclusion and exclusion criteria);
- Documentation of the reason(s) a consented subject is not enrolled

- Participation in study (including study number);
- Study discussed and date of informed consent;
- Dates of all visits;
- Documentation that protocol specific procedures were performed;
- Results of efficacy parameters, as required by the protocol;
- Start and end date (including dose regimen) of IMP, including dates of dispensing and return;
- Record of all adverse events and other safety parameters (start and end date, and including causality and severity);
- Concomitant medication (including start and end date, dose if relevant; dose changes);
- Date of study completion and reason for early discontinuation, if it occurs.

All clinical study documents must be retained by the investigator until at least 2 years or according to local laws, whichever is longer, after the last approval of a marketing application in an ICH region (ie, United States, Europe, or Japan) and until there are no pending or planned marketing applications in an ICH region; or, if no application is filed or if the application is not approved for such indication, until 2 years after the investigation is discontinued and regulatory authorities have been notified. Investigators may be required to retain documents longer if specified by regulatory requirements, by local regulations, or by an agreement with Gilead. The investigator must notify Gilead before destroying any clinical study records.

Should the investigator wish to assign the study records to another party or move them to another location, Gilead must be notified in advance.

If the investigator cannot provide for this archiving requirement at the study site for any or all of the documents, special arrangements must be made between the investigator and Gilead to store these records securely away from the site so that they can be returned sealed to the investigator in case of an inspection. When source documents are required for the continued care of the subject, appropriate copies should be made for storage away from the site.

9.1.6. Case Report Forms

For each subject consented, an eCRF will be completed by an authorized study staff member whose training for this function is documented according to study procedures. eCRF should be completed on the day of the subject visit to enable the sponsor to perform central monitoring of safety data. The Eligibility Criteria eCRF should be completed only after all data related to eligibility have been received. Subsequent to data entry, a study monitor will perform source data verification within the EDC system. Original entries as well as any changes to data fields will be stored in the audit trail of the system. Prior to database lock (or any interim time points

as described in the clinical data management plan), the investigator will use his/her log in credentials to confirm that the forms have been reviewed, and that the entries accurately reflect the information in the source documents. The eCRF capture the data required per the protocol schedule of events and procedures. System-generated or manual queries will be issued to the investigative site staff as data discrepancies are identified by the monitor or internal Gilead staff, who routinely review the data for completeness, correctness, and consistency. The site coordinator is responsible for responding to the queries in a timely manner, within the system, either by confirming the data as correct or updating the original entry, and providing the reason for the update (e.g. data entry error). At the conclusion of the trial, Gilead will provide the site with a read-only archive copy of the data entered by that site. This archive must be stored in accordance with the records retention requirements outlined in Section 9.1.5.

9.1.7. Investigational Medicinal Product Accountability and Return

Where possible, IMP should be destroyed at the site. At the start of the study, the study monitor will evaluate each study center's IMP disposal procedures and provide appropriate instruction for disposal or return of unused IMP supplies. If the site has an appropriate standard operating procedure (SOP) for drug destruction as determined by Gilead Sciences, the site may destroy used (empty or partially empty) and unused IMP supplies as long as performed in accordance with the site's SOP. This can occur only after the study monitor has performed drug accountability during an on-site monitoring visit.

A copy of the site's IMP Disposal SOP or written procedure (signed and dated by the PI or designee) will be obtained for Gilead site files. If the site does not have acceptable procedures in place, arrangements will be made between the site and Gilead Sciences (or Gilead Sciences' representative) for return of unused study drug supplies.

If IMP is destroyed on site, the investigator must maintain accurate records for all IMP destroyed. Records must show the identification and quantity of each unit destroyed, the method of destruction, and the person who disposed of the IMP. Upon study completion, copies of the IMP accountability records must be filed at the site. Another copy will be returned to Gilead.

The study monitor will review IMP supplies and associated records at periodic intervals.

